7.3 LOST TO FOLLOW-UP

After patient discharge from the SNF, study subjects will be considered lost to follow-up if 3 data collection phone calls have been made to the subject with no response.

8 STUDY ASSESSMENTS AND PROCEDURES

8.1 EFFICACY ASSESSMENTS

The procedures and assessments described in this section will be performed at the time point(s) described in the schedule of activities schedule in section 1.3.

All variables will be measured with chart reviews and/or interview-questionnaires with patients and caregivers. Data collection will be identical for intervention and control periods.

Care Transitions Measure-15 (CTM-15)³³

Self-reported preparedness for discharge will be assessed using the CTM-15. It includes 15 questions on a 4-point scale, with a summary score ranging from 0-100. Higher scores are associated with less acute care use after discharge.

This measure will be assessed at 7 days post-discharge, through telephone interview with the patient (or with the patient's legally authorized representative, responding to survey questions as the patient's proxy in cases of patients with cognitive impairment).

Preparedness for Caregiving Scale (PCS)³⁵

Self-reported preparedness for caregiving will be assessed using the PCS. It includes 8 questions on a 5-point Likert scale (0-4), with a range of 0-32. Higher scores are associated with less anxiety.

This measure will be assessed at 7 days post-discharge, through telephone interview with the caregiver.

McGill Quality of Life Questionnaire - Revised (MQoL-R)³⁷

Quality of life across disease trajectories is measured using the MQoL-R. It includes 16 items on a 0-10 point Likert scale.

This measure will be assessed at 30 and 60 days post discharge, through telephone interview with the patient (or with the patient's legally authorized representative, responding to survey questions as the patient's proxy in cases of patients with cognitive impairment).

Life Space Assessment³⁸

Patient function is measured using the Life Space Assessment. It includes 5 Likert scales that correspond to a hierarchy of levels of mobility (each scored 0-4). Weights are the product of the "Life-space Level" (range 1-5) and the "independence" score (range 1-2). Score ranges from 1-120, and lower scores are associated with falls and hospitalization.

This measure will be assessed at 30 and 60 days post discharge, through telephone interview with the patient (or with the patient's legally authorized representative, responding to survey questions as the patient's proxy in cases of patients with cognitive impairment).

Zarit Caregiver Burden Scale^{41,42}

Caregiver burden is measured using the Zarit Caregiver Burden Scale. It includes 12 items on a 5-point scale. Scores range 0-48, and higher scores are associated with depression and social isolation.

This measure will be assessed at 30 and 60 days post-discharge, through telephone interview with the caregiver.

Distress Thermometer²⁸

Caregiver distress is measured using the Distress Thermometer. It includes 1 item on an 11 point scale. Scores range 0-10, with scores >4 associated with poor coping and depression.

This measure will be assessed at 30 and 60 days post-discharge, through telephone interview with the caregiver.

Number of Patient Falls with Injury and Without Injury

This assessment is self-reported by the patient; falls are defined as an "unintentional change in position resulting in a resident coming to rest on the ground or lower level."

This measure will be assessed at 30 and 60 days post discharge, through telephone interview with the patient (or with the patient's legally authorized representative, responding to survey questions as the patient's proxy in cases of patients with cognitive impairment).

MD Visit

This assessment is self-reported by the patient; it is asked in a yes/no question format.

This measure will be assessed at 30 and 60 days post discharge, through telephone interview with the patient (or with the patient's legally authorized representative, responding to survey questions as the patient's proxy in cases of patients with cognitive impairment).

Hospice Enrollment

This assessment is self-reported by the patient; it is asked in a yes/no question format.

This measure will be assessed at 30 and 60 days post discharge, through telephone interview with the patient (or with the patient's legally authorized representative, responding to survey questions as the patient's proxy in cases of patients with cognitive impairment).

Home Health Care Use

This assessment is reported by the nurses and rehabilitation therapists of the patient, as a count of the number of days in home health care.

This measure will be assessed at 30 and 60 days post discharge, through telephone interview with the nurses or rehabilitation therapists.

Hospital Readmissions

This assessment is self-reported by the patient; it is a count of hospital readmissions, either acute or observational stays after SNF discharge.

This measure will be assessed at 30 and 60 days post discharge, through telephone interview with the patient (or with the patient's legally authorized representative, responding to survey questions as the patient's proxy in cases of patients with cognitive impairment).

Emergency Department Use

This assessment is self-reported by the patient; it is a count of emergency department visits without a hospital stay after SNF discharge.

This measure will be assessed at 30 and 60 days post discharge, through telephone interview with the patient (or with the patient's legally authorized representative, responding to survey questions as the patient's proxy in cases of patients with cognitive impairment).

Death Report by Caregiver

This assessment is self-reported by the caregiver regarding patient death after SNF discharge.

This measure will be assessed at 30 and 60 days post discharge, through telephone interview with the caregiver.

Co-variate assessments will be collected in-person and from the medical record. For some caregivers, co-variate data can be collected by phone. Co-variate data are as follows:

- Patient Data collected in person:
 - Study of Osteopathic Fractures Index ¹⁰⁹, measuring frailty of the patient
 - ENRICH Social Support Inventory ¹¹⁰, measuring social support of the patient
- Patient data collected with SNF chart abstraction:
 - Demographics
 - Health insurance status
 - Medical Information
 - Depression (Minimum Data Set section D) ⁹⁴
 - Function (Minimum Data Set section GG) ⁹⁴
 - Cognitive status (Minimum Data Set section C) ^{94, 111}
 - SNF care (i.e., SNF length of stay, urgent or acute treatment while in the SNF)
 - Discharge destination
 - Charlson Comorbidity Index scores ¹¹² (calculated using the problem list in the medical record)
 - Yes or No that the SNF admission date was before the mandated pause in research activities (related to the COVID-19 pandemic)
 - History of COVID-19 diagnosis and treatment in the index hospitalization and/or in the SNF
- Caregiver data collected in-person or by phone:
 - Demographics
 - Relationship to patient
 - Employment
 - Count of days per week providing patient care
 - History of COVID-19 diagnosis and treatment

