2.3 The self-reported combined number of days the patient spends in the ED or hospital in 30- and 60-days post discharge.⁸⁷

2.4 The Zarit Caregiver Burden Scale⁸⁸, assessed at 30- and 60-days post discharge.

2.5 The Distress Thermometer,⁸⁹ assessed 30- and 60-days post discharge.

Study Population:

This study will enroll 360 seriously ill patients in SNFs and 360 caregivers.

Patients must be English speaking, have a minimum data set of 3.0, Section GG Mobility Assessment Score of 3 or less, indicating the patient requires at least 25-50% assistance for functional mobility, be diagnosed with at least 1 serious medical illness, and have a caregiver who can be enrolled in the study.

Caregivers must be English speaking and self-report that they assist the patient at home. For patients with cognitive impairment, documentation in the medical record of a caregiver who is the patient's legally authorized representative, consent of the caregiver to participate in the study as the patient's representative is additionally required.

Phase:

N/A

Description of Sites/Facilities Enrolling Participants:	Six SNFs owned by one organization will participate in this study (none participated in the Connect-Home pilot study). Inclusion criteria for SNFs: location within 120 miles of UNC and at least 15 post-acute admissions per month. Six SNFs and six home health nurses and two alternate SNFs and two alternate home health nurses for each SNF have agreed to participate. If a study site or a home health nurse becomes unavailable to participate, the alternate SNFs and nurses will participate in Connect-Home training.
Description of Study Intervention:	Connect-Home is a two-step transitional care intervention: 1) SNF staff create an individualized Transition Plan or Care and prepare the patient and caregiver to manage the patient's illness at home; and 2) within 24 hours of SNF discharge, a Connect-Home Activation RN visits the patient's home and helps the patient and caregiver implement the written Transition Plan of Care. Both intervention steps focus on 6 key care needs to optimize patient and caregiver outcomes: 1) home safety and level of assistance; 2) advance care planning; 3) symptom management; 4) medication reconciliation; 5) function and activity; and 6) coordination of follow-up medical care.
Study Duration:	This study will be ongoing for four years.

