1.2 SCHEDULE OF ACTIVITIES (SOA)

Schedule of Activities for Patients (Control):

Assessments and Procedures	Screening	Pre-Discharge	Discharge	24 Hours Post-Discharge	7 Days Post-Discharge (+ 10/- 3 days)	30 Days Post-Discharge (+/- 7 days)	60 Days Post-Discharge (+/- 7 days)
Informed Consent	X						
Confirm Eligibility	X						
Study of Osteopathic Fractures Index		X					
ENRICH Social Support Inventory		X					
SNF Chart Abstraction					X		
CTM-15					X		
MQoL-R						X	X
Life Space Assessment						X	X
Falls Assessment						X	X
Hospice Enrollment Assessment						X	X
Home Health Care Chart Abstraction							X
Hospital Use Assessment						X	X
Emergency Department Use Assessment						X	X

Schedule of Activities for Patients (Intervention):

Assessments and Procedures	Screening	Pre-Discharge	Discharge	24 Hours Post-Discharge	7 Days Post-Discharge (+ 10/- 3 days)	30 Days Post-Discharge (+/- 7 days)	60 Days Post-Discharge (+/- 7 days)
Informed Consent	X						
Confirm Eligibility	X						
Study of Osteopathic Fractures Index		X					
ENRICH Social Support Inventory		X					
SNF Chart Abstraction					X		
Connect-Home Intervention in SNF (Step 1)		X					
Connect-Home Intervention in Home (Step 2)				X			
CTM-15					X		
MQoL-R						X	X
Life Space Assessment						X	X
Falls Assessment						X	X
Hospice Enrollment Assessment						X	X
Home Health Care Chart Abstraction							X
Hospital Use Assessment						X	X
Emergency Department Use Assessment						X	X

Schedule of Activities for Caregivers (Control):

Assessments and Procedures	Screening	Pre-Discharge	Discharge	24 Hours Post-Discharge (+3 days)	7 Days Post-Discharge (+/- 2 days)	30 Days Post-Discharge (+/- 7 days)	60 Days Post-Discharge (+/- 7 days)
Informed Consent	X						
Confirm Eligibility	X						
Baseline Questionnaire		X					
Preparedness for Caregiving Scale					X		
Zarit Caregiver Burden Scale						X	X
Distress Thermometer						X	X
Death Assessment						X	X

Schedule of Activities for Caregivers (Intervention):

Assessments and Procedures	Screening	Pre-Discharge	Discharge	24 Hours Post-Discharge (+3 days)	7 Days Post-Discharge (+/- 2 days)	30 Days Post-Discharge (+/- 7 days)	60 Days Post-Discharge (+/- 7 days)
Informed Consent	X						
Confirm Eligibility	X						
Baseline Questionnaire		X					
Connect-Home Intervention in SNF (Step 1)		X					
Connect-Home Intervention in Home (Step 2)				X			
Preparedness for Caregiving Scale					X		
Zarit Caregiver Burden Scale						X	X
Distress Thermometer						X	X

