2.3 RISK/BENEFIT ASSESSMENT

2.3.1 KNOWN POTENTIAL RISKS

Physical Risks:

Patients and caregivers in control periods will receive discharge planning in the SNF, and those in intervention periods will receive transitional care in the SNF and in the patient's home. Discharge planning and transitional care activities involve verbal assessments, conversation, education, and planning. There is a possibility that participants could be fatigued from participation in the data collection activities. For example, while participating in a care-planning meeting, a patient might feel fatigued or need to take a break.

If any participant has a physical injury, the study team will help them seek immediate medical attention. If a SNF patient or caregiver expresses fatigue during data collection, the data collection session will be terminated immediately, and a follow-up appointment scheduled.

Psychological Risks:

Emotional distress related to learning more about medical and functional challenges and plans for care at home is a potential psychological risk. During the control and intervention periods, staff in the SNF and in the home health agency will engage patients and caregivers in conversations to plan strategies for managing the patient's serious illness at home. Also, during enrollment and data collection activities, staff will assess the patients' quality of life, functional mobility, falls at home, days at home without acute care use and caregivers' burden and distress related to the caregiving role. Staff will also review the patient's advance directives. These study-related activities may also involve a chance for emotional distress.

The study team will refer distressed patients and caregivers to their attending or primary care physicians for support with emotional distress.

Social Risks:

During enrollment and data collection activities, study staff will collect data from participants about their health, function and quality of life; if others observed patients or caregivers participating in these activities, there is a chance that it could embarrass or distress patients or caregivers.

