E.4 To assess the patient's number of hospital readmissions (acute or observational stays), 30 and 60 days after discharge from a skilled nursing facility.	E.4 Patient assessment of count of hospital readmissions, assessed 30- and 60-days post discharge.	E.4 All cause re-hospitalizations is the most widely used measure of transitional care interventions. These data will be collected to estimate the representativeness of the study sample and the generalizability of the study findings.
E.5 To assess the patient's number of emergency department visits without a	E.5 Patient assessment of the count of emergency department visits without a	E.5 ED use is a most widely used measure of transitional care interventions. These

OBJECTIVES	ENDPOINTS	JUSTIFICATION FOR ENDPOINTS
hospital stay 30 and 60 days after discharge from a skilled nursing facility.	hospital stay, assessed 30- and 60-days post discharge.	data will be collected to estimate the representativeness of the study sample and the generalizability of the study findings.
E.6 To assess caregiver-reported death of the patient 30 and 60 days after discharge from a skilled nursing facility.	E.6 Caregiver reported death of the patient, assessed 30- and 60-days post discharge.	E.6 Change in the rate of patient death is not an expected study outcome; however, these data will be used to describe the sample.

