The main outcome for Aim 2.3, the number of cumulative days of acute care use, (i.e., days due to re-hospitalizations and emergency department visits), will be modeled using separate marginalized zero-inflated Poisson (MZIP) models with log link. The statistical team will test and estimate the overall effect of Connect-Home relative to standard discharge procedures through exponentiation of the treatment regression coefficient for the overall mean as an incidence rate ratio (IRR) and its 95% confidence interval, basing these on empirical standard errors to allow for possible intraclass correlation within SNFs. MZIP was chosen over the standard ZIP model because although a large number of zero counts (event outcomes) are anticipated, the overall exposure effect of Connect-Home is of interest, and not its effect on an unobserved subpopulation (i.e., latent class). Separate time point-specific generalized linear mixed models (GLMM) with logit link will be used for the binary outcome of whether a resident visited the ED within 30 or 60 days of discharge, respectively, from the SNF. This model type is an extension of ordinary logistic regression that includes random intercepts and period effects for SNFs to account for the within SNF correlation induced by the stepped-wedge design. A similar GLMM will be applied to compare the proportion of hospice referrals between standard discharge procedures and Connect-Home. When events are sparse, SNFs will be treated as fixed effects to mitigate model non-convergence problems.

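### Endpoint 2.3 is defined, powered and modelled in days of ED or hospital use, but Section 8.1 describes only event counts, and the ED outcome in 9.4.3 is broader than the ED measure in 8.1

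*Combined protocol and SAP*

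**What the plan says.** **What the endpoint needs.** The Synopsis and the Section 3 table define endpoint 2.3 as "The self-reported combined number of days the patient spends in the ED or hospital in 30- and 60-days post discharge". Hypothesis 3a in Section 9.1 is about days of acute care use. Section 9.2 powers the comparison in days, and Section 9.4.3 fits a marginalized zero-inflated Poisson (MZIP) model to cumulative days.

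**What is described as collected.** Section 8.1 has two acute-care entries, both by telephone interview at days 30 and 60. For hospital readmissions, "it is a count of hospital readmissions, either acute or observational stays after SNF discharge". For the emergency department, "it is a count of emergency department visits without a hospital stay after SNF discharge". These correspond to exploratory endpoints E.4 ("Patient assessment of count of hospital readmissions, assessed 30- and 60-days post discharge") and E.5, not to endpoint 2.3. The Schedule of Activities lists a "Hospital Use Assessment" and a matching ED item, without saying what either contains.

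**A hint that days are intended.** Section 2.3.1 lists, among the things staff will assess, "functional mobility, falls at home, days at home without acute care use".

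**The ED outcome.** Section 9.4.3 adds a logistic mixed model for the "binary outcome of whether a resident visited the ED within 30 or 60 days of discharge". It does not carry the restriction to visits without a hospital stay found in 8.1 and E.5.

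**Follow-up after an event.** Section 7.2 withdraws a patient who is hospitalized or re-admitted to a SNF after going home, keeps the data gathered before that event, and ends data collection at withdrawal.

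**The concern.** The other four secondary endpoints (quality of life, life space, caregiver burden, caregiver distress) each have an entry in Section 8.1 naming the instrument and how it is obtained. Endpoint 2.3 has none. Nor is the section indifferent to units: its home health entry specifies a number of days. A team that collected exactly what 8.1 describes would finish with the data for E.4 and E.5 and no length of stay for any admission. A one-night observation stay and a two-week admission would look the same. Days of acute care use is the only non-exploratory outcome under Aim 3, with its own hypothesis, power statement and model.

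The ED model has a related problem. If its outcome is meant as any ED visit but is built from the measure in 8.1, a patient who went to the ED and was admitted is coded the same as one who never went. A shift from treat-and-release visits towards admissions would then appear as fewer ED visits.

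**Working it through.** **1. Units, side by side.**

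| Place | Quantity |
|---|---|
| Synopsis and Section 3, endpoint 2.3 | days in ED or hospital |
| Section 9.1, hypothesis 3a | days of acute care use |
| Section 9.2 | days (control mean 4.0 among users) |
| Section 9.4.3, MZIP model | cumulative days |
| Section 8.1, hospital entry; E.4 | number of readmissions |
| Section 8.1, ED entry; E.5 | number of ED visits without a stay |
| Section 9.4.3, logistic model | any ED visit, unqualified |

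The chart abstractions listed in Section 9.4.4 do not fill the gap. The SNF abstraction covers the SNF stay and earlier history, and the home health abstraction gives home health days.

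**2. The plan's own figures reproduce, in days.** Inputs from Section 9.2 for the control group: 22% with at least one day, and a mean of 4.0 days among them. For a zero-inflated Poisson, solve μ/(1 − e^−μ) = 4.0, giving μ = 3.921.
- Overall mean = 0.22 × 4.0 = 0.880 (stated 0.881).
- Excess-zero probability = 1 − 0.22/(1 − e^−3.921) = 0.7755 (stated 0.776).

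Both agree to rounding, which confirms that the calculation assumes data in days.

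**3. The stated 82% power.** With 30% dropout, 360 × 0.70 = 252 patients. A simplified simulation (two groups, independent outcomes, no time trend, Wald test on the log ratio of means, 4,000 runs) used the plan's means and excess-zero probabilities. It gives about 84.5% to 85.5% for splits of 126/126, 115/137 and 117/135. The plan's simulation model is not fully specified, so the 82% is not disputed.

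**4. Counts do not determine days.** Take a patient with one readmission and one ED visit, counting one day per ED visit (assumed). Days = length of stay + 1. A 1-day stay gives 2 days and a 7-day stay gives 8 (assumed range). The recorded counts are identical.

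**5. What the counts do recover of the days variable.** If every stay or visit is worth at least one day, the counts show whether days are zero or not. With ν the overall mean and ψ the excess-zero probability, P(any use) = (1 − ψ)(1 − e^−ν/(1−ψ)).
- Control: 0.224 × (1 − e^−0.881/0.224) = 0.2196, or 22.0%.
- Intervention: 0.315 × (1 − e^−1.8/0.315) = 0.3140, or 31.4%.
- Difference: 0.3140 − 0.2196 = 0.0944.

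For a two-sided 5% test with 126 per group under independence, the pooled proportion is 0.2668. The standard error is √(2 × 0.2668 × 0.7332/126) = 0.0557 under the null and √((0.2196 × 0.7804 + 0.3140 × 0.6860)/126) = 0.0554 under the alternative. Power ≈ Φ((0.0944 − 1.96 × 0.0557)/0.0554) = Φ(−0.27) ≈ 0.39.

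So about 39%, against the stated 82% for days under independence, or about 85% from the simplified simulation in step 3.

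**6. The ED outcome.** There are two readings. If Section 9.4.3 means visits without a stay, it agrees with 8.1 and E.5 and lacks only the qualifier. If it means any ED visit, the described measure misses patients whose only ED contact ended in admission. The documents do not give the share of admissions that come through the ED, so no size is attached.

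**7. Withdrawal.** Even with a days item, a patient withdrawn at the first hospitalization under Section 7.2 contributes no further days. Read literally, the rule may exclude the stay that triggered the withdrawal, since only data collected before the event are kept.

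**The case against.** The strongest reply is that Section 8.1 is a summary and not the instrument. The endpoint is itself defined as self-reported days, Section 2.3.1 says that time at home without acute care is assessed, and the schedule labels are broad enough to cover a days question. On that view the entry for endpoint 2.3 was simply left out. This has force. A reader might infer from 8.1 that days are not collected and that the endpoint is lost. The documents do not support that: they show that the described measures cannot yield days, and the interview forms are not in the file. What stands is that the one section describing the measurements disagrees with the endpoint, and that nowhere is a respondent, question or counting rule for days given.

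A second reply is that admissions are recorded elsewhere. Inpatient hospitalization is a serious adverse event (Section 8.2.2), and adverse events are recorded and followed to resolution (Sections 8.2.4 and 8.2.5). That provides a second record of admissions, but those sections promise no admission or discharge dates.

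Third, a reader might conclude that the ED model certainly misclassifies admitted patients. It does so only if any ED visit is meant. The matching definitions in 8.1 and E.5 make the narrower reading plausible, and an admitted patient is still captured by the readmission count.

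Fourth, the wording of the ED entry already keeps an ED visit and its resulting admission from both being counted as events. That is correct for counts. It does not say how many days a treat-and-release visit contributes, or how days are totalled.

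**Conclusion.** The point holds as an internal conflict. Endpoint 2.3 is defined, powered and modelled in days, while the acute-care measures described in 8.1 are counts from which days cannot be computed. Days are probably intended, and the documents do not prove that they go uncollected.

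If only the counts were collected, the recoverable part of the days variable (any use or none) would have about 39% power, against the stated 82%. That figure rests on the plan's assumed means and excess-zero probabilities, 126 patients per group, independence within SNFs, and each event counting as at least one day. It is used for size only. The plan assumes more acute care days under intervention (1.8) than under control (0.881), the reverse of hypothesis 3a; that is a separate matter.

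It would go too far to say that Aim 3 would be left with no outcome, because hypothesis 3a also names hospice enrollment, as exploratory. The ED point is conditional on what Section 9.4.3 means, and its size cannot be set from the documents. This should be settled before data collection relies on 8.1, because a powered secondary endpoint currently has no described data source.

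**What to change.** - **Section 8.1 and the day-30 and day-60 calls:** add an entry for endpoint 2.3. Record admission and discharge dates (or length of stay) for each hospital or observation stay, and the date and disposition of each ED visit. If the interview forms already ask for this, describe it in 8.1.
- **Counting rule:** state how an ED visit counts toward days. One option is the number of distinct calendar days with any ED or hospital care through day 30 and through day 60.
- **ED definition:** use one definition in 8.1, E.5 and 9.4.3, either any ED visit or ED visit without a hospital stay.
- **Section 7.2:** reconcile the withdrawal of hospitalized patients with endpoint 2.3, which the rule would truncate even with a days item in place.

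The cost is a few extra questions for patients who report an event, so slightly longer calls for that group, plus wording changes in four sections (3, 7.2, 8.1 and 9.4.3).
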